3.0 TRIAL OBJECTIVES AND PURPOSE

3.1 Primary Objectives

1. To compare the complete response rate, defined as the proportion of patients who achieve CR, and duration of CR with APR-246 + azacitidine treatment vs. azacitidine only.

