8.2 Efficacy Assessments

The primary endpoint is CR per the modified IWG (Cheson et al, 2006; see [Appendix II](#)) and time between achieving CR and relapse of disease.

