8.2.1 Duration of Response

Duration of response (DOR) is measured from the time of initial response to disease **relapse**/progression or death.

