9.0 STATISTICS

9.1 Sample Size

This trial will include 154 patients with 77 patients randomized in a 1:1 ratio to each of the two treatment arms (APR-246 + azacitidine treatment versus azacitidine treatment alone).

If the true CR rate is 50% for the treatment arm and 25% for the control arm, the trial will have 90% power to detect a statistically significant effect in favor of the APR-246 at a 2-sided alpha = 0.05 significance level.

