9.2 Analysis Populations

Intent-to-Treat (ITT) population: All patients who are randomized on study will be considered eligible for the ITT population and will be used for demographics, baseline characteristics summaries. The ITT population will be the primary analysis population for efficacy.

Efficacy-Evaluable (EE) population: All patients who complete at least one treatment cycle of APR-246 and azacitidine and who have at least one post-treatment clinical response assessment. Patients who fail to complete one post-treatment clinical response assessment will also be considered EE if they show clear evidence of clinically significant disease progression. The EE population will be the secondary analysis population for efficacy.

Safety population: Patients will be evaluable for safety if they receive at least one dose of APR-246 or azacitidine. The safety population will be used to summarize exposure and safety parameters.

Pharmacokinetics: Patients will be evaluable for pharmacokinetics if at least one sample for PK evaluation has been obtained.

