9.3 Statistical Methods

9.3.1 Efficacy Analyses

Primary endpoint CR will be summarized for all randomized patients (ITT) as the proportion of patients (%) with CR. CR will be compared between treatment arms using a Cochran-Mantel-Haenszel (CMH) test stratified by age (< 65 years versus ≥ 65 years). In addition to presenting the CR rate and associated exact 95% CI for each treatment arm, the treatment effect will be described using the CMH estimate of the common odds ratio together with its associated 95% CI.

Duration of response (DOR) is defined as the time from the date when criteria for

response) are met to the date of relapse, progression, or death due to any cause, whichever occurs first. Patients alive without relapse or progression will have their DOR censored at the date of the last clinical assessment. The duration of CR will be summarized in each treatment arm by providing the median DOR together with associated 95% CI, using Kaplan-Meier methodology.

Overall response will be summarized in number (%) of patients in each category of responses (CR, PR, mCR with HI, mCR without HI, HI). ORR will be analyzed by using the similar method as primary endpoint CR. DOR, as defined above, will also be evaluated in regards to ORR.

Time to AML is calculated from first day of study treatment to first onset of AML. Kaplan-Meier methodology will be utilized. Rate of AML transformation will be analyzed by using the same method as primary endpoint CR.

Survival data are collected at treatment and follow-up periods. Patients will be followed until death. Overall Survival (OS) is defined as the number of days from the date of randomization to the date of death. Kaplan-Meier methodology will be utilized.

Relapse-free survival (RFS) is defined as the time from the date of randomization to disease relapse, progression or death from MDS, whichever occurs first. If neither event occurs, RFS will be censored at the date of the last assessment. Kaplan-Meier methodology will be utilized.

Time to AML, OS and RFS will be analyzed using the similar methods as DOR.

Transition rate to SCT will be analyzed using the similar methods as complete response rate.

Important subgroup analyses will be detailed in the Statistical Analysis Plan.

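### Duration of CR is part of the primary objective's between-arm comparison, but its only planned analysis is a median among patients who reach CR, which is not a randomised comparison and can mislead in either direction

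*Combined protocol and SAP*

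**What the plan says.** Section 3.1 states the primary objective as "To compare the complete response rate, defined as the proportion of patients who achieve CR, and duration of CR" on the combination against azacitidine only. Section 8.2 gives the matching second part of the primary endpoint as "time between achieving CR and relapse of disease".

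In section 9.3.1 the duration clock starts when response criteria "are met to the date of relapse, progression, or death due to any cause, whichever occurs first". A patient without CR has no value on this scale. The analysis is then: "The duration of CR will be summarized in each treatment arm by providing the median DOR together with associated 95% CI", by Kaplan-Meier. No test, hazard ratio or difference between arms is named for CR duration. The same section defers subgroup analyses to a Statistical Analysis Plan but says no such thing about duration.

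Section 9.2 says: "The ITT population will be the primary analysis population for efficacy". It does not say how randomised patients without CR enter the duration part of the objective. Section 8.2.3 plans inverse probability of censoring weights, but for transplant only. Overall survival and relapse-free survival start at randomisation; both are secondary, and neither measures time in CR.

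The sample size in section 9.1 rests on the CR rate alone: "If the true CR rate is 50% for the treatment arm and 25% for the control arm".

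**The concern.** The objective asks for a comparison, and two Kaplan-Meier medians are all a reader will have to make it with. The patients behind them were not formed by randomisation. If APR-246 raises the CR rate as planned, its CR group includes patients who would not have reached CR on azacitidine alone, and these have no counterpart in the control CR group. The two medians then differ for two reasons that cannot be separated: an effect on the length of remission, and a different mix of patients.

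At stake is how half of the primary objective is read. A combination that shortens nobody's remission could show the lower median beside a positive CR result. Equally, one that lengthens nobody's remission could show the higher median. Settling the end event and the censoring rule would not remove this, and neither would adding a hazard ratio in the same patients, because the comparison set itself depends on treatment. Stratifying randomisation by more factors would not remove it either.

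**Working it through.** **1. The plan's own figure.** Inputs from section 9.1: p1 = 0.50, p2 = 0.25, two-sided alpha 0.05, power 90%, 1:1. With pooled variance under the null and mean rate 0.375:

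n per arm = [1.960 × √(2 × 0.375 × 0.625) + 1.282 × √(0.25 + 0.1875)]² / 0.25² = (1.342 + 0.848)² / 0.0625 ≈ 76.7, so 77 per arm and 154 in total. Power at 77 per arm is 90.1%. The stated design reproduces, and nothing below affects it.

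**2. Size of the CR groups.** Expected CRs: 77 × 0.50 = 38.5 against 77 × 0.25 = 19.25. Assume that everyone who reaches CR on azacitidine would also do so on the combination (the documents do not state this). Then 38.5 − 19.25 = 19.25 of the APR-246 CRs, half of them, are added responders.

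**3. Illustrative durations.** The base median is 7 months, from a Table 1 footnote. It is the duration of any response in TP53-mutant patients, used as a stand-in for CR duration. Durations are taken as exponential. Patients who respond on either arm keep the 7-month median in both arms, so no remission is shortened or lengthened. Added responders have median m, which is assumed.

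- APR-246 responder median t solves 0.5 × 2^(−t/7) + 0.5 × 2^(−t/m) = 0.5.
- Mean months in CR within 12 months of CR, for a group with median m: R(m) = (m / ln 2) × (1 − 2^(−12/m)).
- Per randomised patient, with 0 for no CR: control 0.25 × R(7) = 0.25 × 7.02 = 1.76; APR-246 0.25 × R(7) + 0.25 × R(m).

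Two cases can be solved by hand. For m = 3.5, put x = 2^(−t/7); then x² + x = 1, x = 0.618 and t = 7 × 0.694 = 4.9. For m = 14, put x = 2^(−t/14); the equation is the same and t = 14 × 0.694 = 9.7.

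| Added responders' median m (months) | Responder median, APR-246 v control | Mean months in CR per randomised patient, APR-246 v control |
|---|---|---|
| 2.3 | 3.8 v 7.0 | 2.56 v 1.76 |
| 3.5 | 4.9 v 7.0 | 2.90 v 1.76 |
| 5 | 5.9 v 7.0 | 3.22 v 1.76 |
| 7 | 7.0 v 7.0 | 3.51 v 1.76 |
| 14 | 9.7 v 7.0 | 4.02 v 1.76 |

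With 5.7 months as the base (the other TP53-mutant response duration in the Table 1 footnotes), m = 2, 3, 4 and 5 give responder medians of 3.2, 4.1, 4.8 and 5.3 against 5.7.

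**4. How often a trial of this size shows it.** Simulation of 4,000 trials per scenario, 77 per arm, CR at about 3 months, and an assumed 18-month accrual with at least 15 months of follow-up. For m = 7, 5, 3.5 and 2.3 months, repeated runs put the APR-246 median below control in 46–49%, 64–67%, 80–82% and 90–92% of trials.

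The plan names no log-rank test. If one were added among CR patients, it would be significantly against APR-246 in about 2%, 7–8%, 16–17% and 27–28% of trials. For m = 14 it would falsely favour APR-246 in 20–21%.

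**5. What the all-randomised measure does and does not show.** Mean time in CR to 12 months, scored 0 without CR, two-sided 5% test:

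- No effect on rate or duration: significant for APR-246 in 2.6% of trials.
- CR 50% v 25%, no effect on duration: significant for APR-246 in 73–74%.
- CR 50% v 25%, every remission shortened (hazard ratio 1.5): still significant for APR-246 in 39–40%.

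**The case against.** **The plan contains no biased test.** Section 9.3.1 describes a per-arm summary, and the only comparative test named for the primary endpoint is the stratified CMH test of CR in all randomised patients. A reader might infer from the log-rank figures that the planned analysis has an inflated error rate. The documents do not support that; those figures show only that adding a test in the same patients would not help. What remains is that the objective says compare and nothing else in the plan supplies a comparison of CR duration.

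**The direction is assumed.** A reader might infer that the plan is biased against APR-246. No section says that added responders have shorter remissions; with equal durations the effect vanishes, and with longer ones it reverses. The background shows that prognosis varies within TP53-mutant disease (section 2.2: median survival 124 days with allele frequency above 40%, not reached below 20%), so unequal durations are plausible. It does not settle the sign.

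**The all-randomised measure answers another question.** This stands. It mixes CR rate with duration, as step 5 shows. A reader might take it for a better test of whether APR-246 prolongs remission; it is not one, because it can favour a treatment that shortens every remission.

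**Survival endpoints give context.** They do, since both start at randomisation, but neither measures time in CR.

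**Conclusion.** The concern holds in a limited form. The duration part of the primary objective has no comparison protected by randomisation, and the two responder medians that stand in for it can differ through patient mix alone. That the comparison is not randomised follows from the plan's definitions and its assumed CR rates.

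The size and sign do not follow from the documents. The figure of about 65% to 90% of trials with a lower APR-246 median depends on a 7-month base median, exponential durations, every azacitidine responder also responding on the combination, and added responders with medians of 5 to 2.3 months. Other assumptions give no effect or the opposite one. The CR rate test, its population and its power are untouched. This is an inexpensive improvement to the analysis plan; it does not undermine the design.

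**What to change.** In section 9.3.1:

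1. State that the Kaplan-Meier medians among CR patients are descriptive within arm and are not the between-arm comparison of CR duration.
2. Add an analysis in all randomised patients: the probability-of-being-in-CR curve by arm, and the age-stratified difference in mean time in CR to a fixed horizon, scored 0 for patients without CR, with a 95% CI (bootstrap or Wald). Fix the horizon before data are seen, for example 18 months from randomisation or 12 months from first CR.
3. State its limit: it combines CR rate and duration, is driven largely by the rate, and is a net-benefit measure read beside the CR rate and the descriptive medians. It is not a test that APR-246 prolongs remission.

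The cost is protocol and SAP wording and one added analysis of data already collected. Sample size, the CMH test and the visit schedule do not change.

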	
APR-246 + azacitidine treatment vs. azacitidine only. Secondary Objectives: To measure the following with APR-246 + azacitidine treatment vs. azacitidine alone:
 
 1. Overall response rate (ORR) 2. Duration of response (DOR) 3. Rate and time to acute myeloid leukemia (AML) transformation 4. Overall survival (OS) 5. Relapse-free survival (RFS) 6. Transition rate to hematopoietic stem cell transplant (HSCT) 7. Safety profile 8. Rate of red blood cell (RBC) and/or platelet transfusion independence (TI) for 56 days (8 weeks) 9. Pharmacokinetics of APR-246 and azacitidine 
Exploratory Objectives:
 
 1. Determine if biomarkers predictive for response to therapy can be derived from baseline molecular analyses of bone marrow or blood samples 2. Determine the depth of remission by IHC, PCR, and other techniques in serial bone marrow or blood samples 3. Investigate potential resistance mechanisms by molecular analysis of bone marrow or blood samples at disease progression 
VAF

Study Endpoints
	
Primary Endpoint: CR per the modified IWG (Cheson et al, 2006)¹ and time between achieving CR and relapse of disease. Secondary Endpoints:
 
 1. ORR is the proportion of patients achieving hematological improvement (HI), partial remission (PR), CR, marrow CR by the IWG 2006 criteria 2. Response duration 3. AML transformation according to World Health Organization (WHO) criteria 4. OS 5. RFS 6. Proportion of patients who transition to HSCT 7. Safety endpoints can relate to adverse events, serious adverse events, dose adjustments or dose holds, lab parameter values, vital signs, ECGs 8. Patients who achieve RBC and/or platelet TI during the 56-day (8 week) period after randomization 9. Pharmacokinetic endpoints: C_{max} (maximum concentration), AUC (area under the curve), Vd and clearance (CL) of APR-246 and azacitidine 
Exploratory Endpoints:
 
 1. Baseline molecular analyses may include, but are not limited to: TP53 VAF by NGS, p53 immunohistochemistry, mutations in other genes by NGS, RNA expression 2. Investigations of depth of remission may include, but are not limited to: PCR and p53 immunohistochemistry 3. Molecular analyses at disease progression may include, but are not limited to: TP53 VAF by NGS, p53 immunohistochemistry, mutations in other genes by NGS, RNA expression

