Duration of response (DOR) is defined as the time from the date when criteria for response are met to the date of progressive disease or death due to any cause, whichever occurs first. Patients alive with no progressive disease will have their DOR censored at the date of the last clinical assessment. The duration of CR will be summarized in each treatment arm by providing the median DOR together with associated 95% (CI), using Kaplan-Meier methodology.

Overall response will be summarized in number (%) of patients in each category of responses (CR, PR, mCR with HI, mCR without HI, HI). ORR will be analyzed by using the similar method as primary endpoint CR. DOR, as defined above, will also be evaluated in regard to ORR. Time to AML is calculated from first day of study treatment to first onset of AML. Kaplan-Meier methodology will be utilized. Rate of AML transformation will be analyzed by using the similar method as primary endpoint CR.

Survival data are collected at treatment and follow-up periods. Patients will be followed until death. Overall survival (OS) is defined as the number of days from the date of randomization to the date of death. Kaplan-Meier methodology will be utilized.

Relapse-free survival (RFS) is defined as the time from the date of randomization to disease relapse or death from MDS, whichever occurs first. If neither event occurs, RFS will be censored at the date of the last clinical assessment. Kaplan-Meier methodology will be utilized.

Time to AML, OS and RFS will be analyzed using the similar methods as DOR.

Transition rate to HSCT will be analyzed using the similar methods as primary endpoint CR.

Safety Analyses

Safety data including adverse events, vital signs, laboratory data, ECG, physical exam will be tabulated for the safety population. Adverse events will be tabulated by body system, preferred term, severity, and relationship to treatments. The tabulation of laboratory parameters will include the normal ranges for each parameter. Each value will be classified as falling above, below, or within the normal range. Laboratory parameters will also be tabulated by maximum NCI-

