2. DOR
3. Rate and time AML transformation
4. Overall survival (OS)
5. Relapse-free survival (RFS)
6. Transition rate to hematopoietic stem cell transplant (HSCT)
7. Safety profile
8. Rate of red blood cell (RBC) and/or platelet transfusion independence (TI) for 56 days (8 weeks)
9. Pharmacokinetics of APR-246 and azacitidine

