7.6 Long-Term Follow-Up

This can be done remotely (e.g. via telephone, via General Practitioner or via review of medical records).

Assuming there is no withdrawal of consent, patients who stop study treatment (APR-246 or azacitidine) for any reason (e.g. toxicity, transition to SCT, PD) will continue long-term follow-up:

1. Patients who discontinue study treatment to receive SCT:
 - a. Collect post SCT response assessments, transformation to AML and survival every month until relapse or death, whichever occurs first.
 - b. After PD, collect data for survival and transformation to AML every 6 months until death.
2. Responders (CR, PR, mCR with HI, mCR without HI, HI) who discontinue study treatment for other reasons than progressive disease or SCT:
 - a. Collect response assessments, transformation to AML and survival monthly until relapse or death, whichever occurs first.

- b. After relapse/progression, continue collecting data for survival and transformation to AML every 6 months until death.
3. Non-Responders: patients who discontinue study treatment due to progressive disease:
 - a. Collect data for survival and transformation to AML every 6 months until death.

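### The only named between-arm AML test is a CMH test on a proportion with no time horizon, so it mixes the effect on AML with the effect on death before AML

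*Combined protocol and SAP*

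**What the plan says.** AML transformation is a secondary objective, listed in section 3.2 as "Rate and time AML transformation". The synopsis endpoint is "AML transformation according to World Health Organization (WHO) criteria", with no landmark or window.

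For the rate, section 9.3.1 says "Rate of AML transformation will be analyzed by using the same method as primary endpoint CR"; the synopsis statistics section says "Rate of AML transformation will be analyzed by using the similar method as primary endpoint CR". The method being borrowed is: "CR will be compared between treatment arms using a Cochran-Mantel-Haenszel (CMH) test stratified by age (< 65 years versus ≥ 65 years"). The denominator for CR is all randomized patients: it is "summarized for all randomized patients (ITT) as the proportion of patients (%) with CR".

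On follow-up, section 9.3.1 says "Patients will be followed until death". After progression, section 7.6 has sites "collect data for survival and transformation to AML every 6 months until death". Responders and transplanted patients are contacted monthly until relapse or death.

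For the time component, section 9.3.1 plans Kaplan-Meier for time to AML, handled like DOR: a median and 95% CI per arm. No between-arm test, no rule for death before AML and no data cut for the AML analyses are given. CMH is thus the only between-arm AML comparison that the plan names.

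**The concern.** CR is reached early or not at all, so a yes/no analysis suits it. AML accrues for as long as the patient is alive and observed, and death removes patients from risk. Both events are common here: section 2.2 puts median OS near 8 months, and section 2.1 puts progression to AML at about 70% in higher-risk disease.

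A crude proportion then depends on three things: the AML hazard, the hazard of death without AML, and how long patients have been followed. At stake is whether the trial can show a real slowing of AML, and whether a difference in the AML proportion can be read as an effect on AML at all.

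**Working it through.** **The plan's own figure.** The only sample-size figure is for CR (section 9.1): 50% vs 25%, two-sided 0.05, 90% power. With pooled variance and no continuity correction, n = [1.960·√(2×0.375×0.625) + 1.2816·√(0.25+0.1875)]² / 0.25² = (1.342 + 0.848)² / 0.0625 = 76.7, so 77 per arm. This reproduces the plan, and power at 77 is 90.1%. No rate or power is given for AML.

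**Inputs.** From the documents: 77 per arm, two age strata, and a projected duration of 30-36 months (section 4.5), used as the data cut. Assumed: constant hazards; control median AML-free survival of 8 months (borrowed from the OS figure in section 2.2); uniform 18-month accrual; AML as first event in 40-70% of controls if all were followed to an event; 30% of patients under 65 (23 and 54 per arm); and the hazard ratios.

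**What the odds ratio estimates.** Let a be the AML hazard, d the hazard of death without AML, and λ = a + d. With complete follow-up the proportion ever transforming is a/λ and its odds are a/d, so the odds ratio is HR(AML) / HR(death without AML):
- both HR 0.6: 0.6/0.6 = 1.00
- death only HR 0.6: 1/0.6 = 1.67
- AML only HR 0.6: 0.6/1 = 0.60

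**At a data cut C with accrual A.** P = (a/λ)·{1 − [e^(−λ(C−A)) − e^(−λC)]/(λA)}. For a 40% AML share, the control λ is ln2/8 = 0.0866 per month. At C = 30 and A = 18, P = 0.4·{1 − [0.354 − 0.074]/1.560} = 0.328. The other entries follow in the same way.

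| Scenario (40% share) | 30 months, APR-246 vs control | OR | 36 months | OR | To death, OR |
|---|---|---|---|---|---|
| AML and death HR 0.6 | 26.1% vs 32.8% | 0.72 | 29.8% vs 35.7% | 0.76 | 1.00 |
| Death only HR 0.6 | 38.6% vs 32.8% | 1.29 | 43.2% vs 35.7% | 1.37 | 1.67 |

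In each row the hazard effects are fixed, yet the odds ratio moves with the cut.

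**Simulated trials at 30-36 months.** Each trial was analysed by two-stratum CMH and by a stratified log-rank test on AML, censoring at death without AML. The ranges span repeat runs and so include simulation error.

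| Scenario | Finding | CMH | Cause-specific log-rank |
|---|---|---|---|
| Both HR 0.6, share 40% | AML benefit | 12-14% | 39-44% |
| Both HR 0.6, share 70% | AML benefit | 25-29% | 60-67% |
| Death only HR 0.6, share 40-70% | excess AML | 8-17% | about 2.5% |
| Death only HR 0.8, share 40-70% | excess AML | 4-7% | about 2.5% |
| AML only HR 0.6, share 40% | AML benefit | 32-35% | 35-40% |
| AML only HR 0.6, share 70%* | AML benefit | 48-50% | 59-64% |

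*Run with a 7.6-month median, and 24-month accrual for the 36-month cut.

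With no effect on either hazard, both tests reject at about 5% two-sided.

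**The case against.** The strongest reply is that CMH is not making an error. If deaths before AML fall, more patients really do transform, and CMH detects a real difference in absolute risk, which is a legitimate meaning of a rate. Aalen-Johansen curves would show the same excess. This stands: the excess is a real rise in cumulative incidence, but it is not an effect on the AML hazard. The plan provides no analysis that separates the two.

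A reader might infer a false safety signal whenever APR-246 prolongs survival. The documents do not support that. AML transformation is an efficacy endpoint and is not part of the safety analysis in section 9.3.3. Longer survival after AML leaves the proportion unchanged; only fewer deaths before AML raise it. Nothing in the documents shows such a selective effect.

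A reader might also quote larger distortions, such as 25% false excess or 7% vs 49% power. Those need about 54 months (18 months of accrual plus 36 of minimum follow-up), against a projected 30-36. Follow-up to death would permit a later cut, but none is scheduled.

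Kaplan-Meier curves for time to AML, with OS beside them, would give some view of a delay. That helps, but no between-arm comparison is attached to time to AML. Finally, equal hazard ratios are a hard case for CMH; when only AML is slowed it loses much less. That also stands.

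**Conclusion.** The concern holds in limited form. The planned AML odds ratio is not an estimate of the effect on AML alone, and its value depends on an unstated length of follow-up. The main cost at 30-36 months is power when APR-246 slows AML and death together: the loss to the cause-specific log-rank is roughly 25 to 40 percentage points. Excess AML declared without any change in the AML hazard is a smaller problem, and close to nominal if the effect on death is modest.

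The direction of these results follows from the algebra. Their sizes rest on constant hazards and on the assumed AML share, accrual, median and hazard ratios, none of which the documents give for this trial. AML transformation is one of nine secondary objectives, with no alpha or power attached. The point merits a change to the plan but does not threaten its main conclusion.

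**What to change.** In section 9.3.1 and the synopsis:

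1. Make the between-arm AML comparison an age-stratified cause-specific log-rank test for time to AML, with hazard ratio and 95% CI, treating death without AML as the competing event.
2. Replace the crude proportion with Aalen-Johansen cumulative incidence of AML and of death without AML, side by side, at a fixed time. Twelve months is one option: with 18-month accrual and a 30-month cut, every patient has at least 30 − 18 = 12 months of potential follow-up. The absolute risk should stay in the report, since it answers a real question. Cumulative incidence alone is not enough, because it also rises when competing deaths fall.
3. Report AML-free survival (AML or death) as support, and state the data cut.

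The cost is wording and one more table; AML and death dates are already collected. There are two downsides. The cause-specific result must be read beside the death curve. AML dates are also less precise in patients contacted every 6 months after progression than in responders contacted monthly (section 7.6), and a time-based test is more exposed to that than a yes/no count. The open-label design is a reason to settle this before outcome data are reviewed.

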Sallman *et al.* performed an internal analysis of molecularly profiled patients at Moffitt Cancer Center and also identified that the clonal burden, or variant allele frequency (VAF), had significant impact on clinical phenotype and more importantly further stratified prognosis over binary mutational analysis alone and/or clinical prognostic models²³. Specifically, MDS patients with a TP53 VAF > 40% had a median overall survival (OS) of 124 days versus an OS that was not reached in patients with VAF < 20% (hazard ratio (HR), 3.52; P = 0.01) with validation in an independent cohort (HR, 4.94, P = 0.01). Overall, TP53 mutant MDS and AML patients have a median OS ranging from 5-9 months with 8 months representing the best estimate when restricting to MDS and oligoblastic AML (20-30% blasts) (Figure 1)^{20,23,24;25,26}.

[figure not shown]

Figure 1. Historical Overall Survival for *TP53* Mutant MDS/AML ($\leq 30\%$ blasts) Treated with Frontline Azacitidine (Source: Moffitt Cancer Center Database).

Median OS of 7.6 Months in MDS/AML patients treated with frontline AZA (n=51).

Together, these data highlight the dismal outcomes of *TP53* mutant patients and the dire need for the development of novel therapeutic strategies, particularly in this patient population.

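### RFS has two conflicting event lists and leaves deaths not from MDS to be censored, and time to AML has no rule for death before AML

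*Combined protocol and SAP*

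**What the plan says.** RFS and time to AML are secondary endpoints. Each is defined twice, in the synopsis (Statistics, Efficacy Analyses) and in section 9.3.1.

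- **RFS, 9.3.1:** "Relapse-free survival (RFS) is defined as the time from the date of randomization to disease relapse, progression or death from MDS, whichever occurs first". Without an event, "RFS will be censored at the date of the last assessment".
- **RFS, synopsis:** "time from the date of randomization to disease relapse or death from MDS, whichever occurs first". Without an event, "RFS will be censored at the date of the last clinical assessment".
- **DOR, 9.3.1:** from the date response criteria "are met to the date of relapse, progression, or death due to any cause, whichever occurs first". The synopsis version lists progressive disease or death from any cause and does not name relapse.
- **Time to AML, both places:** "Time to AML is calculated from first day of study treatment to first onset of AML. Kaplan-Meier methodology will be utilized". No censoring rule follows, and death before AML is not mentioned.
- **Cross-reference:** "Time to AML, OS and RFS will be analyzed using the similar methods as DOR".

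The rate of AML transformation is analysed separately as a proportion, by the same CMH approach as CR.

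**The concern.** Two analysts following the plan could report different RFS results. RFS runs from randomisation in every patient, but Appendix II defines relapse only after CR or PR, or after HI. A patient who never responds cannot relapse. If that patient progresses, 9.3.1 records an event, and the synopsis records nothing unless and until the patient dies from MDS.

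Both versions also rest on a judgement about cause of death. Read literally, a death not attributed to MDS is not an event, so the patient is censored at the last assessment. The supplied text gives no rule for the attribution and describes no adjudication, and the trial is open label. Transplant makes this concrete. Section 8.2.3 links SCT with good response, and the design assumes CR rates of 50% and 25%, so transplant-related deaths could differ between arms. Nothing says how such deaths are classed.

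For time to AML, death without AML is a competing event in a population with high early mortality. If those deaths are censored, one minus the Kaplan-Meier estimate describes AML risk as though nobody died first, which overstates the proportion who develop AML.

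**Working it through.** **The plan's own figure.** The only design calculation is for CR: 50% against 25%, two-sided alpha 0.05, 90% power. With mean proportion 0.375, n per arm = [1.960 × √(2 × 0.375 × 0.625) + 1.282 × √(0.5 × 0.5 + 0.25 × 0.75)]² / 0.25² = 76.7, so 77 per arm and 154 in total. Power at 77 per arm is 90.1%. The stated size reproduces and does not depend on RFS or AML.

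**RFS definitions side by side.**

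| Patient | Synopsis | 9.3.1 |
|---|---|---|
| Never responds, progresses, later dies from MDS | Event at death | Event at progression |
| Never responds, progresses, later dies from another cause | Censored | Event at progression |
| Responds, dies in remission from another cause | Censored (though a DOR event) | Censored (though a DOR event) |

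The censoring dates differ by one word (clinical). Section 7.6 allows remote follow-up, so the difference matters only if a remote survival contact counts as an assessment. The documents do not say, and no effect on a result can be shown.

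**RFS, size of the cause-of-death restriction.** The documents give no share of deaths not from MDS, so this is assumed, with constant hazards.

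- Assume median time to relapse or progression of 9 months and to death without relapse of 16 months. The hazards are ln2/9 = 0.0770 and ln2/16 = 0.0433 per month.
- All-cause median = ln2/(0.0770 + 0.0433) = 5.76 months.
- If a share s of those deaths is not from MDS, the median becomes ln2/(0.0770 + 0.0433 × (1 − s)). For s = 10% this is 5.98 months (×1.04). For s = 40% it is 6.73 months (×1.17).
- If instead a share f of all first events is non-MDS death, the ratio is 1/(1 − f): ×1.11 at 10% and ×1.43 at 30%. On the hazards above, deaths are 0.0433/0.1203 = 36% of first events, so f = 30% would need 0.30/0.36 = 83% of deaths to be non-MDS.
- With identical all-cause hazards in both arms, but a non-MDS share of 10% in one arm and 20% to 40% in the other, the apparent hazard ratio is 0.96 to 0.89 in favour of the arm with the larger share.

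**Time to AML, size.** Let a be the AML hazard, assumed 0.02 to 0.06 per month, and d the hazard of death without AML.

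- One minus Kaplan-Meier = 1 − exp(−a t).
- Cumulative incidence = a/(a + d) × [1 − exp(−(a + d) t)].

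Section 2.2 gives median OS of 12.4 months (one Table 1 study) and 7.6 months (Figure 1 note), so d = ln2/12.4 = 0.0559 or ln2/7.6 = 0.0912. Both include deaths after AML and so overstate d. Half of 0.0559, that is 0.0279, is the more cautious case.

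| d per month | Time (months) | 1 − KM | Cumulative incidence | Excess (points) |
|---|---|---|---|---|
| 0.0279 | 12 | 21.3–51.3% | 18.2–44.5% | 3.1–6.8 |
| 0.0279 | 24 | 38.1–76.3% | 28.5–60.0% | 9.6–16.4 |
| 0.0559 | 12 | 21.3–51.3% | 15.8–38.9% | 5.5–12.4 |
| 0.0912 | 12 | 21.3–51.3% | 13.2–33.2% | 8.1–18.1 |

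**AML clock.** It starts at first treatment, so it is undefined for randomised patients who are never dosed, although they belong to the ITT population. Each is 1/154 = 0.6%. Few are expected, since 7.2.2 randomises patients when they are ready to start. This is minor.

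**The case against.** Counting only deaths from MDS is the Appendix II wording for PFS, so it may be deliberate. That stands as an explanation. But Appendix II does not define RFS, and the same list gives event-free survival with death from any cause.

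The missing progression event looks like a synopsis that was not updated, because DOR shows the same drift: relapse is named in 9.3.1 and not in the synopsis. That is plausible, but both texts are current and neither is said to prevail. It also means DOR is not free of the problem. Section 9.3.1 defers only subgroup analyses to the SAP, so nothing indicates that these points are settled there.

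On AML, the plan nowhere says that one minus Kaplan-Meier will be reported as incidence. The CMH rate keeps early deaths in its denominator and is not inflated this way. A cause-specific hazard ratio would also censor deaths, legitimately. All of this stands: the overstatement arises when the curve is read as risk.

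Four stronger readings are tempting, and the documents do not support them.

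- A reader might infer that the cross-reference imports DOR's death rule and turns time to AML into AML-free survival. The same sentence covers OS and RFS, which have their own events, so Kaplan-Meier with deaths censored is the coherent reading.
- A reader might use non-responders in Table 1, from 3/13 × 77 = 18 to 23/38 × 77 = 47 per arm, as a ceiling on the patients affected by the progression mismatch. It is not one. It removes every overall responder, yet Appendix II defines no relapse after marrow CR without HI.
- A reader might infer bias towards the experimental arm. The direction depends on how non-MDS deaths fall between arms, which is unknown.
- A reader might infer that cause of late death is not collected. The follow-up items listed are survival and AML, but the CRF and the body of the evaluation schedule are not in the supplied text.

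**Conclusion.** The point holds for secondary endpoints and should be fixed before analysis. The two RFS event lists conflict. Both leave non-MDS deaths to be censored on an attribution that the supplied text does not define. Time to AML has no rule for death before AML, and its natural reading overstates incidence.

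The sizes are illustrations under constant, assumed hazards. Median RFS is inflated roughly ×1.04 to ×1.17 if 10% to 40% of deaths without relapse are non-MDS, and ×1.11 to ×1.43 only if 10% to 30% of all first events are. AML incidence is overstated by about 3 to 7 points at 12 months and 10 to 16 at 24 in the cautious case, and by more with full OS hazards. The primary CR test, the sample size of 154 and OS are unaffected. No power or alpha is stated for RFS or time to AML.

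**What to change.** - **RFS:** put one definition and one censoring date in the synopsis and 9.3.1: randomisation to relapse, progression or death from any cause. Relabelling it progression-free or event-free survival is optional.
- **DOR:** in the same edit, bring the synopsis event list into line with 9.3.1.
- **Time to AML:** start at randomisation in the ITT population. Estimate by cumulative incidence (Aalen-Johansen) with death without AML as a competing event, and say so in place of the cross-reference to DOR. Keep the CMH comparison of the AML rate. A cause-specific hazard ratio is optional.

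The cost is protocol and SAP wording and a little more analysis in standard software. Dates of death and AML transformation are already listed for collection (schedule footnote o), with survival and AML followed under section 7.6. Counting all deaths removes the need to attribute cause. The downside is a shorter reported median RFS.
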